4.0 Eligibility Criteria

Inclusion Criteria

• The target sample of participants will be children, ages 14-48 months referred to the EE Hubs due to a screen-positive result on the MCHAT-R/F and/or parent/caregiver or pediatric provider concerns about development.

Exclusion Criteria

• Children must have a parent/caregiver(s) who speaks English to them such that 1) they are exposed to spoken language in English or 2) the child speaks and/or understands English. Given age and disability of children in the study, some children may not yet have developed functional receptive or expressive language. However, children who do not meet the above criteria will not be included in this research due to the significant language demands of study procedures and some assessments not being validated in languages other than English.

5.0 Study Design

This study uses a quantitative experimental design to address the specific aims. Please see the following diagram for a description of design.

6.0 Enrollment/Randomization

Subjects will be identified by the EE Hubs. Parent/caregiver(s) of a consecutive sample of children (ages 14-48 months) will be given a study information brochure and asked if they are interested in learning more about the study. If interested, parent/caregiver(s) will fill out a contact information sheet, which will be sent to the research coordinator. The research coordinator will contact the parent/caregiver(s) by phone/email to provide additional information about the study. If the parent/caregiver(s) agree to participate, the research coordinator will schedule the research visit. Written informed consent and authorization (to share evaluation results between EE Hub, child's primary care, and research team will be obtained at the time of the appointment.

Blinded Evaluation Process: Because the family will have received an initial diagnosis for their child during the evaluation at the EE Hub, there is risk for the family to share this information with the blinded ASD specialist, thereby introducing bias into the final diagnostic decision. In order to mitigate this bias, families will be informed on several occasions (i.e., at the time of referral, during the consenting process, and by the blinded ASD-specialist) that they are not to share their child's EE Hub diagnosis with the ASD specialist.

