7.0 Study Procedures

Children (ages 14-48 months) are referred to the EE hub by their primary care provider when there is concern about a neurodevelopmental disability (e.g., parent/PCP concern or failed developmental screener; i.e., MCHAT-R/F). Children are evaluated by a pediatric health professional at the EE Hub with a standard battery of developmental history, physical exam, and behavioral measures; a diagnosis is made when appropriate and the parent/caregiver(s) receive the diagnosis and next step recommendations. For the purpose of this study, the pediatric health professional will complete a diagnostic certainty form indicating whether or not they provided a diagnosis of autism spectrum disorder and how certain they are about the diagnostic outcome [1-5 Likert scale; 1=completely certain; 5=not at all certain].

The EE Hubs will refer a consecutive sample of children for follow-up evaluation by study personnel (diagnostic evaluation overseen by PI/ASD Specialist: [name]). The EE Hub pediatric health professional will provide the parent/caregiver(s) with information about the study via a study brochure. If the parent/caregiver(s) is interested in participating, the parent will complete and sign the contact information sheet and it will be sent to the study team. The research coordinator will contact the parent/caregiver(s) by phone to provide additional information about the study. If the parent/caregiver(s) agrees to participate, the research coordinator will schedule a follow-up evaluation, at no cost to the child's family, at the local EE Hub site. This follow-up visit will occur within 16 weeks of the original EE Hub evaluation. During this call, the parent/caregiver(s) will provide verbal consent to have a battery of caregiver-report questionnaires sent to them by mail or via secure electronic link (i.e., Redcap) to return prior to or at the time of the research visit. This process will reduce face-to-face time required for the research visit.

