Informed consent will occur at the start of the research visit. The parent/caregiver (or current legal guardian) will sign the HIPAA authorization form allowing the EE Hub to share evaluation data (MCHAT or MCHAT-R/F, ASQ-3, and STAT scores), diagnosis, and diagnostic certainty ratings with the study personnel and for the study personnel to provide research evaluation data back to the participant's primary care physician and EE Hub physician. The research visit will last for a duration of 3 hours, during which an ASD specialist (and/or other study personnel under the direction of an ASD specialist) will: 1) conduct a semi-structured clinical interview to gather developmental history, DSM-5 symptoms of ASD, and related medical/ neurodevelopmental information, 2) administer the Autism Diagnostic Observation Schedule-2 and Mullen Scales of Early Learning to the child, 3) administer the Vineland Adaptive Behavior Scales (Vineland-II) to the parent/caregiver of the child, 4) request that the parent/ caregiver complete symptom/behavior rating scales and a brief demographic questionnaire if not completed prior to the visit (as described above). The ASD specialist will also complete the same

diagnostic certainty form (as above), 5) complete a brief sensory processing assessment (SPA), and 6) collect a brief sample of eye-tracking data (~15mins; see below).

Eye-tracking data will be collected using a remote eye-tracking system (SR Research, Eyelink Portable Duo), which is placed in front and below the stimulus presentation monitor. Eye movements and pupil diameter will be collected while participants view a series of pictures and movies. The modular system is completely non-invasive with no hardware on or touching participants (only a small sticker is placed on their forehead). A camera monitors eye movements while a second scene camera monitors head movements, allowing eye-tracking to take place without a chin rest or bite bar. Children will be asked to sit on a chair or on their caregiver's lap and will face a computer monitor. After the sticker is applied to participant's forehead and brief calibration completed, visual stimuli will be presented on a laptop computer monitor that is placed at approximately 60cm from the participant. Brightness will be at a comfortable viewing level. The eye tracking portion of the visit will last approximately 15 minutes. All study procedures and data collection will occur at the EE Hub sites.

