14.0 Privacy/Confidentiality Issues

Individuals with access to study data and information will be limited to the PI and the PI's specific designees. A number or a letter string will refer to all subjects. No personal identifying information will be stored with responses. All records will be labeled using the number identification of a particular subject only. There will be dissociation of participant coding and specific identifier information. The key to this coding will be kept separate in a password protected document separate from other data and/or under two locks in a devoted cabinet. Electronic data will be stored on a computer protected by a password, HIPAA compliant firewalls, and backed up on the server. Paper documents will be kept in a cabinet in a locked office of [name] [name]. At termination of the study, paper copies of data will be maintained or shredded and scanned copies kept on a secure server for the requisite time period. Names and any identifying information will not be used in any presentations or publications that may result from this study.

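### The protocol text does not say that Hub results are withheld from the specialist until the reference diagnosis is recorded, and does not provide for recording disclosure or examining Aim 1 by it

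*Combined protocol and SAP*

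**What the plan says.** Section 6.0 (Blinded Evaluation Process) states the risk: "there is risk for the family to share this information with the blinded ASD specialist, thereby introducing bias into the final diagnostic decision". Its remedy is to tell families, at referral, at consent and through the specialist, that "they are not to share their child's EE Hub diagnosis with the ASD specialist". No other safeguard appears in the text.

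Section 7.0 adds the following:

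- At the start of the research visit the caregiver signs an authorization for the Hub to share its screening scores, "diagnosis, and diagnostic certainty ratings with the study personnel".
- The research assessment is described as a "diagnostic evaluation overseen by PI/ASD Specialist" and is carried out by an ASD specialist, by other study personnel under a specialist's direction, or by both. It includes a caregiver interview to "gather developmental history, DSM-5 symptoms of ASD, and related medical/ neurodevelopmental information".
- The specialist completes the same certainty form as the Hub clinician. As described, that form holds the diagnosis (ASD or not) and a 1 to 5 certainty rating.
- Caregiver questionnaires may be returned before or at the visit. Section 3.0 lists among the caregiver measures a satisfaction form about the Hub visit.
- Where the two diagnoses differ, the specialist contacts the child's providers.

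Section 12.0 plans sensitivity, specificity, predictive values and kappa with a 95% confidence interval for Aim 1. The specialist's diagnosis is also the outcome for Aim 3.

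**The concern.** Aim 1 measures agreement, so the reference diagnosis has to be made without knowledge of the result it is compared with. The protocol recognises this and addresses what families say. It does not address how the Hub's own results are handled once the authorization is signed, and it leaves no trace when the instruction to families fails.

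The second gap matters more. Some disclosure has to be expected when a caregiver who already has a diagnosis is interviewed about the child's development. Whether it happened can be noted reliably only at the visit. Afterwards the specialist learns the Hub result in at least the discordant cases, so a later question about what was known beforehand would be unreliable. Without a record, the study could neither show that its agreement is free of this bias nor put a bound on it.

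**Working it through.** **Plan's own figure.** There is none on this point. The documents give no expected agreement for this study, no disclosure rate and no target for kappa. The power statements in section 12.0 concern odds ratios in logistic regression and do not bear on it.

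**The text set side by side.**

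| Question | What the text provides |
|---|---|
| Are families asked not to tell? | Yes, on three occasions (6.0) |
| Who may receive Hub scores, diagnosis and certainty? | Study personnel; the specialist is not excepted (7.0) |
| When may the specialist see them? | Not stated (7.0) |
| Must the reference diagnosis be recorded first? | Not stated (7.0) |
| Is the caregiver form about the Hub visit kept from the specialist? | Not stated (3.0, 7.0) |
| Is disclosure recorded? | Not in the form as described (7.0); the instruments are in attachments (13.0, 17.0) |
| Is Aim 1 examined by blinding status? | No (12.0) |

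**Illustration of size.** Inputs:

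- 120 children, 60 with and 60 without ASD (section 12.0).
- Agreement *A* without disclosure, taken as 80% and equal in both groups. This is assumed. Section 1.0 reports 71% to 93% in earlier small studies.
- Share of visits unblinded, *u*, and share *w* of the otherwise discordant calls at those visits that follow the Hub. Both are assumed; the documents give neither.

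With a 50/50 split and equal error rates, chance agreement is 0.50, so:

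- discordance *D* = (1 − *A*) × (1 − *u* × *w*)
- kappa = 1 − 2 × *D*

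| *u* | *w* | *D* | kappa |
|---|---|---|---|
| 0 | any | 0.20 | 0.60 |
| 0.20 | 0.5 | 0.20 × 0.90 = 0.18 | 0.64 |
| 0.20 | 1 | 0.20 × 0.80 = 0.16 | 0.68 |
| 0.40 | 0.5 | 0.20 × 0.80 = 0.16 | 0.68 |
| 0.40 | 1 | 0.20 × 0.60 = 0.12 | 0.76 |

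At *u* = 0.20, with *w* from 0.5 to 1, the other anchors give:

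- *A* = 71%: kappa rises from 0.42 to between 0.48 and 0.54.
- *A* = 87%: kappa rises from 0.74 to between 0.77 and 0.79.

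**Could the data show it?** At kappa 0.60, the standard error is √[0.80 × 0.20 / (120 × 0.50²)] = 0.073, and the 95% half-width is 1.96 × 0.073 = 0.14. At *u* = 0.20 the shift is 0.04 to 0.08, inside that margin. The agreement table alone therefore cannot separate such a shift from chance.

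**The case against.** Much can be said for the plan. It names the bias, calls the specialist blinded, and repeats the instruction at three points. Several stronger readings are tempting, and the documents do not support them.

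- *The authorization gives the specialist the Hub result.* It is a permission to share, in a plan that calls the specialist blinded. It does not say who opens the data or when. It is signed at the start of a 3-hour visit, the certainty form is listed among that visit's activities, and results are given verbally after the evaluation. Any formal window looks short, and contact about discordant diagnoses presupposes that a research diagnosis exists.
- *The principal investigator sets every reference diagnosis with Hub data in hand.* Section 7.0 says the investigator oversees the evaluation. Section 14.0, "Individuals with access to study data and information will be limited to the PI and the PI's specific designees", is a confidentiality rule. Neither establishes who makes each diagnosis or what that person has seen.
- *The caregiver interview is a further unguarded channel.* It is the family channel that section 6.0 already addresses, and the reference evaluation includes it by design.
- *No breach is recorded anywhere.* The forms are in attachments not reviewed, and the design diagram is not shown. Only the protocol text and analysis plan can be judged.
- *Agreement will be inflated.* That is the expected direction if the specialist is drawn toward the Hub result. It is not an established fact, and the rates used above are assumed.

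These points limit the concern but do not remove it. The text still lacks a rule on timing, a provision for recording disclosure, and an analysis that uses such a record. The small size of the plausible shift does not help the plan either, because a shift of that size would pass unnoticed.

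**Conclusion.** The concern holds as a gap in the protocol text and analysis plan. Instructions to families are the only stated safeguard. Withholding of Hub results until the reference diagnosis is recorded is not stated. Neither a disclosure record nor an Aim 1 analysis by blinding status is provided for in what was reviewed.

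The documents do not show that blinding fails or that the specialist sees Hub results early. The size of any bias cannot be derived from them. A kappa rising from 0.60 to between 0.64 and 0.68 is an illustration that rests on 80% agreement, a 50/50 split, equal error rates, 20% of visits unblinded, and half to all of the otherwise discordant calls at those visits following the Hub.

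The change should be made, because unrecorded disclosure cannot be recovered later and the remedy costs little. It does not call the design into question. Confidence is medium, since the attachments may already hold part of the remedy.

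**What to change.** 1. **Release rule (sections 6.0 and 7.0).** State that Hub scores, diagnosis and certainty rating, and the caregiver form about the Hub visit, go to the research coordinator only. State that they are withheld from the specialist until the specialist's diagnosis and certainty form are completed and time-stamped.
2. **One form item.** Ask the specialist, on the same form, whether the Hub diagnosis became known before the decision (yes or no) and, if so, how.
3. **Analysis (section 12.0, Aim 1).** Report the disclosure rate, and repeat the Aim 1 indices without disclosed visits as a pre-specified sensitivity analysis.

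An item asking the specialist to guess the Hub diagnosis is best left out, or its accuracy should not be read as evidence of unblinding. A fully blinded specialist would sensibly guess their own diagnosis and be right at about the agreement rate, which is 80% in the illustration.

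The cost is a few sentences, one form item and one extra analysis, with no added visits or staff. If an attachment already covers items 1 or 2, it is enough to state so in the protocol and add item 3.

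There are two downsides. The sensitivity analysis has a smaller sample: with 20% of visits excluded, 120 becomes 96, and the kappa half-width at 80% agreement goes from 0.14 to 1.96 × √[0.16 / (96 × 0.25)] = 0.16. Excluding disclosed visits may also select on diagnosis or severity, so the analysis supports the main result and does not replace it.

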7.0 Study Procedures

Children (ages 14-48 months) are referred to the EE hub by their primary care provider when there is concern about a neurodevelopmental disability (e.g., parent/PCP concern or failed developmental screener; i.e., MCHAT-R/F). Children are evaluated by a pediatric health professional at the EE Hub with a standard battery of developmental history, physical exam, and behavioral measures; a diagnosis is made when appropriate and the parent/caregiver(s) receive the diagnosis and next step recommendations. For the purpose of this study, the pediatric health professional will complete a diagnostic certainty form indicating whether or not they provided a diagnosis of autism spectrum disorder and how certain they are about the diagnostic outcome [1-5 Likert scale; 1=completely certain; 5=not at all certain].

The EE Hubs will refer a consecutive sample of children for follow-up evaluation by study personnel (diagnostic evaluation overseen by PI/ASD Specialist: [name]). The EE Hub pediatric health professional will provide the parent/caregiver(s) with information about the study via a study brochure. If the parent/caregiver(s) is interested in participating, the parent will complete and sign the contact information sheet and it will be sent to the study team. The research coordinator will contact the parent/caregiver(s) by phone to provide additional information about the study. If the parent/caregiver(s) agrees to participate, the research coordinator will schedule a follow-up evaluation, at no cost to the child's family, at the local EE Hub site. This follow-up visit will occur within 16 weeks of the original EE Hub evaluation. During this call, the parent/caregiver(s) will provide verbal consent to have a battery of caregiver-report questionnaires sent to them by mail or via secure electronic link (i.e., Redcap) to return prior to or at the time of the research visit. This process will reduce face-to-face time required for the research visit.

Informed consent will occur at the start of the research visit. The parent/caregiver (or current legal guardian) will sign the HIPAA authorization form allowing the EE Hub to share evaluation data (MCHAT or MCHAT-R/F, ASQ-3, and STAT scores), diagnosis, and diagnostic certainty ratings with the study personnel and for the study personnel to provide research evaluation data back to the participant's primary care physician and EE Hub physician. The research visit will last for a duration of 3 hours, during which an ASD specialist (and/or other study personnel under the direction of an ASD specialist) will: 1) conduct a semi-structured clinical interview to gather developmental history, DSM-5 symptoms of ASD, and related medical/ neurodevelopmental information, 2) administer the Autism Diagnostic Observation Schedule-2 and Mullen Scales of Early Learning to the child, 3) administer the Vineland Adaptive Behavior Scales (Vineland-II) to the parent/caregiver of the child, 4) request that the parent/ caregiver complete symptom/behavior rating scales and a brief demographic questionnaire if not completed prior to the visit (as described above). The ASD specialist will also complete the same

diagnostic certainty form (as above), 5) complete a brief sensory processing assessment (SPA), and 6) collect a brief sample of eye-tracking data (~15mins; see below).

Eye-tracking data will be collected using a remote eye-tracking system (SR Research, Eyelink Portable Duo), which is placed in front and below the stimulus presentation monitor. Eye movements and pupil diameter will be collected while participants view a series of pictures and movies. The modular system is completely non-invasive with no hardware on or touching participants (only a small sticker is placed on their forehead). A camera monitors eye movements while a second scene camera monitors head movements, allowing eye-tracking to take place without a chin rest or bite bar. Children will be asked to sit on a chair or on their caregiver's lap and will face a computer monitor. After the sticker is applied to participant's forehead and brief calibration completed, visual stimuli will be presented on a laptop computer monitor that is placed at approximately 60cm from the participant. Brightness will be at a comfortable viewing level. The eye tracking portion of the visit will last approximately 15 minutes. All study procedures and data collection will occur at the EE Hub sites.

Participants will be compensated with a gift card in the amount of \$25 per hour of completed research testing (up to a maximum of \$75). The average length of the evaluation is estimated to be 3 hours. This hourly amount includes any travel related expenses. If participants choose to withdraw from the study, they will be compensated for the length of their participation (at the above rate of \$25 per hour).

Results of the evaluation will be provided to the child's parent/caregiver(s) verbally following the evaluation. A brief report summarizing results of the evaluation and research diagnosis will be provided to the child's parent/caregiver(s), primary care physician, and the EE Hub physician (as appropriate with authorization). In cases where the diagnosis differs between the EE Hub and ASD specialist, the ASD specialist will contact the child's primary care provider and EE Hub provider (when written authorization is provided) by phone, fax, and/or secure email to discuss difference in diagnosis and to help the provider identify next steps in the child's care. The child's family will be offered further consultation by a neurodevelopmental specialist through Riley Hospital for Children neurodevelopmental subspecialists if desired/indicated (provided and billed as a medical service).

Caregivers will be sent a secure electronic link (i.e., Redcap) to complete the Intervention and Service Questionnaire at 3, 6, 12, 18, and 24 months following their research evaluation. If there is no response within 1 week of survey deployment, the research team will reach out by phone to ask caregivers if they would prefer to complete the survey verbally by phone. This survey is estimated to take less than 30 minutes to complete. Caregivers will be reimbursed with a \$15 gift card for every time point a survey is completed.

8.0 Study Calendar

Day 1: Study team receives written authorization to contact parent/caregiver of child who received evaluation in EE Hub

Within 2-14 days*: Study team contacts parent/caregiver by phone to provide information

	and conduct initial eligibility screening; follow-up evaluation scheduled for children of parent/caregivers who provide verbal agreement; caregiver report questionnaires sent to caregiver for completion (by mail or secure electronic link) prior to the research visit
Within 16 weeks*:	Follow-up evaluation is conducted at EE Hub by ASD specialist and study team
Within 18 weeks*:	Written research evaluation report is provided to child's parent/caregiver, EE Hub physician, and PCP
16 wks + 3 months:	3-month Intervention and Service Questionnaire sent to caregivers.
16 wks + 6 months:	6-month Intervention and Service Questionnaire sent to caregivers.
16 wks + 12 months:	12-month Intervention and Service Questionnaire sent to caregivers.
16 wks + 18 months:	18-month Intervention and Service Questionnaire sent to caregivers.
16 wks + 24 months:	24-month Intervention and Service Questionnaire sent to caregivers.

*Times are relative to Day 1.

9.0 **Reportable Events**

AE's or unanticipated problems will be reported by the PI to the IU IRB (following the KC Reportable Events procedures; https://research.iu.edu/training/guides/human-subjects/kuali-coeus-irb/submit-reportable-event.html) within 5 business days of the study team becoming aware of the event.

Monitoring of AE's or unanticipated problems will begin at the time of informed consent. AE's or unanticipated problems applicable to this study may include:

- 1. Adverse event assessed by the principal investigator (PI) as (1) unexpected, (2) related or possibly related to study participation, AND (3) suggests that the research places subject(s) or others at greater risk of harm than was previously known.
- 2. Unanticipated adverse device effects.
- 3. Subject complaints that indicate an unexpected risk and/or that affect the rights and welfare of human subjects.
- 4. Incidents that may compromise information security, subject privacy, and/or confidentiality (e.g., subject data breach).

All other AE's and unanticipated problems as outlined in IU's policy (found at: https://research.iu.edu/compliance/human-subjects/guidance/reportable.html) will be reported to the appropriate monitoring board(s) as specified.

